Appendix J Schedule of Procedures and Observations

Schedule of Procedures and Observations

Evaluation	Baseline ¹	Day - 14	Each Cycle Day 1	Each Cycle Day 15	End of Cycle 1	Day 1 of Cycle 5 and every 4 th cycle thereafter	End of Treatment	Follow-Up ²
Medical History with Pre-existing Conditions	X ¹							
Physical Examination ⁴ and/or vital signs ⁵	X ³	X ^{4,5}	X ^{4,5}	X ⁵		X ^{4,5}	X ^{4,5}	
Hematology ⁶	X	X	X ⁷	X ⁷		X	X	
Chemistry ⁸	X	X	X ⁸	X ⁸		X	X	
Pregnancy Test (Urine)	X ^{1a}							
ECOG Performance Status	X	X	X				X	
HLA Typing	X ^{1b}							
IPSS/ IPSS-R (Appendix E and Appendix F)	X ²⁰					X	X	

PROTOCOL TITLE: I 49217 - Phase 1 CDX-1401/ Poly-ICLC +Decitabine +Nivolumab in Patients with MDS or Low Blast Count AML

Evaluation	Baseline ¹	Day - 14	Each Cycle Day 1	Each Cycle Day 15	End of Cycle 1	Day 1 of Cycle 5 and every 4 th cycle thereafter	End of Treatment	Follow-Up ²
HIV, HBV, HBC	X ¹⁹							
Response Assessment (Appendix D, Appendix E, Appendix F) and TTT						X	X	
Bone Marrow Aspirate and Biopsy ⁹	X				X ¹⁸	X	X ¹⁴	X ²¹
Endocrine Function Evaluation ¹⁷ : TSH	X				X			
Cardiac Safety Markers ¹⁵	X ^{1a}				X			
Electrocardiogram ¹⁶	X ^{1a}				X			
Echocardiogram ^{16a}	X ^{1a}							
Urinalysis	X ^{1a}				X	X		
Research Samples								
Correlative Blood Sampling	X ¹²	X ¹²	X ¹²			X ¹²	X ¹²	X ¹²
Bone Marrow Aspirate	X ¹³				X ¹³	X ¹³	X ^{13,14}	X ¹³
Study Drugs								
CDX-1401/ Poly-ICLC injection		X ^{10,11}		X ^{10,11}		X ^{10,11}		
Decitabine			Day 1 through Day 5 of each treatment cycle ^{10 a}					
Nivolumab			Day 1 and Day 15 of each treatment cycle ^{10 b}					
Concomitant Medications	X ¹	X	X			X	X	X
Adverse Events		X	X	X	X	X	X	X
Survival Status								X

- 1 Performed within 4 weeks prior to first dose of CDX-1401/poly-ICLC) unless otherwise indicated.
1a: Performed within 3 week prior to first dose of CDX-1401/poly-ICLC) unless otherwise indicated
1b: Patients who do not require HLA typing for determination of transplant eligibility will have HLA typing sent for study purposes: Each site will perform their own HLA analysis according to institutional guidelines. **Samples taken at RPCI:** 1, 10 mL lavender-top tube to be sent to RPCI Immune Analysis Facility c/o [[name]](#), [name], [name]).
- 2 Performed 30 days, 60 days, 90 days, and 180 days (± 3 days) following last dose of study drug (last immunization with CDX-1401/poly ICLC/nivolumab). Assessment may be collected via telephone if the patient elects to come off study and is no longer coming to clinic.
- 3 Height collected at baseline only.
- 4 Physical examination on day -14 and day 1 of each cycle (or up to 3 days prior to the beginning of a cycle) and at end of treatment
- 5 Vital signs including temperature, heart rate, oxygen saturation, respiratory rate, body weight and blood pressure prior to CDX-1401/poly ICLC dosing on day -14 and day 15 of each cycle (cycles 1-4) or day 1 of each 4th cycle (cycles 5+) and prior to decitabine dosing on day 1 of each cycle
- 6 CBC with manual differential

PROTOCOL TITLE: I 49217 - Phase 1 CDX-1401/ Poly-ICLC +Decitabine +Nivolumab in
Patients with MDS or Low Blast Count AML

- 7 Once per week each cycle during cycles 1-4, from cycles 5 onward on Day 1 and as clinically indicated. Used to assess hematologic improvement per modified International Working Group criteria for MDS on Day 1 every cycle 1.
- 8 CMP, LDH, uric acid, amylase and, lipase. Once per week each cycle during cycles 1-4 and, on Day 1 from cycle 5 and onward and, as clinically indicated.
- 9 Bone Marrow Aspirate and Biopsy, Flow Cytometry, Conventional Cytogenetics+/- FISH as appropriate. At the end of cycle 1 a Bone Marrow aspirate is to be done purely for collection of correlative specimens, unless the patient has demonstrated sufficient clinical response to warrant disease assessment at the discretion of the treating physician. **Note:** At the end of Cycle 1, if a bone marrow aspirate is not able to be done, a bone marrow biopsy may be performed instead. Thereafter a complete bone marrow assessment to be done every 4th cycle (per standard of care) for response assessment. If bone marrow is unable to be obtained due to dry tap, collected 4 additional green top tubes of peripheral blood.
- 10 **CDX-1401/poly-ICLC** administered on day -14 of cycle 1 and then *day 15 of every cycle for the first 4 cycles.*
NOTE: After Cycle 4: to be given on *day 1 of every 4th cycle as a booster (i.e. on day 1 of cycles 8, 12, 16, 20, 24).*
10a: Decitabine administered on days 1-5 of each cycle.
10b: Nivolumab administered every 2 weeks on days 1 and 15 of each cycle for the first 4 cycles.
Note: After Cycle 4: to be given on day 1 of every cycle 5 and above
- 11 Following administration of the CDX-1401/poly ICLC patients will be observed for 1 hour and undergo temperature, blood pressure and heart rate monitoring every 30 minutes.
- 12 Study blood work includes the following: At Baseline: Six green top tubes, 1 gold top tube; Cycle 1 day - 14: 6 green top tubes, 1 gold top; Cycles 1-4 once weekly: 6 green top tubes; Cycles 5-end of study, every 2 weeks: 6 green tops and 1 gold top (see section 11.11.1). If it is determined that there is an inadequate cell number for cryopreservation and immunomonitoring, at any visit, sample acquisition may be repeated at the next scheduled blood draw.
- 13 Study Bone marrow samples for T-cell and methylation and gene expression studies, 4 green tops tubes to be obtained each time a bone marrow assessment is to be done (see Section 11.11.2).
- 14 End of study bone marrow may be done +/- 14 days from day 29 of the last cycle of decitabine for convenience.
- 15 Troponin-I, CK-MB, will be obtained at baseline (within 4 weeks prior to first dose of study drug) and at the end of Cycle 1 and as clinically indicated.
- 16 Electrocardiogram will be performed at baseline and at the end of Cycle 1 and as clinically indicated.
16^a: Echocardiogram will be performed at baseline or anytime as clinically indicated.
- 17 For **endocrine function monitoring:** Follow up- 6-8 weeks with repeat labs (may be done sooner if patient is symptomatic): refer to Endocrinology if abnormal labs. If patient is symptomatic, start initial treatment (most commonly thyroid replacement and/or hydrocortisone): always replace steroids first and thyroid hormone a few days later to prevent worsening of adrenal insufficiency. In cases of thyroiditis (low TSH, high free T4), treat symptomatically with beta-blockers and refer to Endocrinology. Note: Some patients with hypophysitis will require high dose steroids with taper and MRI pituitary. Refer to Appendix H for immune-related adverse event management guidelines.
- 18 At the end of cycle 1 a Bone Marrow aspirate is to be done purely for collection of correlative specimens (see Section 11.9.2) unless the patient has demonstrated sufficient clinical response to warrant disease assessment at the discretion of the treating physician. **Note:** At the end of Cycle 1, if a bone marrow aspirate is not able to be done, a bone marrow biopsy may be performed instead. Thereafter, a complete bone marrow assessment to be done every 4th cycle (per standard of care) for response assessment.
- 19 Testing for HIV I/II Ab, HBsAg, HCV Ab+/- PCR should be done only in patients for whom there is a concern for prior infection with one of these viral pathogens. Testing is NOT required if there is no history of infection.
- 20 Refer to Appendix E and Appendix F for calculation instructions.
- 21 Bone marrow biopsy per institutional guidelines for patients on study < 2 years. Bone marrow biopsy every 6 months (\pm 2 months) for patients on study for \geq 2 years with correlative samples. Correlative samples to be collected at any time point when patient has a bone marrow biopsy for standard of care.

PROTOCOL TITLE: I 49217 - Phase 1 CDX-1401/ Poly-ICLC +Decitabine +Nivolumab in
Patients with MDS or Low Blast Count AML

PROTOCOL TITLE: I 49217 - Phase 1 CDX-1401/ Poly-ICLC +Decitabine +Nivolumab in
Patients with MDS or Low Blast Count AML

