10.1 Dosing and Administration

The vaccine is comprised of CDX-1401 (1 mg) given intracutaneously with 1.8 mg of Poly-ICLC. The first dose of the vaccine is given on Day -14 and then, on Day 15 of each decitabine cycle for the first 4 cycles (total of 5 vaccines). Thereafter, patients will receive a booster vaccine on Day 1 of every 4th cycle, indefinitely.

Nivolumab is to be given at a fixed dose of 3 mg/kg every 2 weeks starting on Day 1 of Cycle 1 through cycle 4 day 15. After cycle 5 nivolumab will be given as a flat dose of 480mg every 4 weeks on day 1 of each decitabine cycle (+/-7 day window). Nivolumab administration may continue on protocol until disease progression or the patient elects to discontinue nivolumab.

Decitabine/nivolumab cycles will be given on schedule every 4 weeks unless a delay is deemed clinically necessary by the treating physician/investigator. If the patient requires a delay of more than 6 weeks, they will come off study. The study schema is depicted in **Figure 3**.

Figure 3: Study Schema

For the purposes of this study, 1 cycle = 28 days and is comprised of 5 doses of IV decitabine (days 1-5), 2 doses of nivolumab during cycles 1-4 and 1 dose of nivolumab cycles 5 and above (day 1 and day 15 during cycles 1-4 or day 1 cycles 5 and above) and 1 vaccination (day 15). Protocol therapy may be given at the discretion of the treating physician within a +/-7 day window to accommodate patient’s preference, clinical judgement and schedule or outside this window after discussion with the PI.

Note: When nivolumab and decitabine are administered on the same day, decitabine is administered first, followed by nivolumab.

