10.1.1 Vaccine (Anti DEC-205-NY-ESO-1 Fusion Protein (CDX-1401)/ Poly ICLC)

CDX-1401 and poly-ICLC will be administered on Day -14 prior to the first course of decitabine and *then Day 15 of every cycle for the first 4 cycles. After Cycle 4*, CDX-1401 and poly-ICLC will

PROTOCOL TITLE: I 49217 - Phase 1 CDX-1401/ Poly-ICLC +Decitabine +Nivolumab in Patients with MDS or Low Blast Count AML

be administered on Day 1 of every 4th cycle as a booster (i.e. on day 1 of cycles 8, 12, 16, 20, 24) (see study calendar below: Section 10.1.3).

The CDX-1401 will be given as an intracutaneous injection (a mixture of subcutaneous and intradermal administration, at a dose of 1 mg); poly-ICLC will be given subcutaneously at a flat dose of 1.8 mg on each day of CDX-1401 vaccination.

Administration: Within a vaccine treatment session (consisting of one intracutaneous administration of CDX-1401 with poly-ICLC) dosing should be given within the same administration site (a 5 x 5 cm area on the extremities or the abdomen). The administration site should be free of potentially complicating dermatologic conditions, and should not be located in an area where integrity of the draining lymph node bed is potentially compromised (i.e., an extremity where a nodal resection was previously performed). For each subsequent administration session, a new administration site should be selected, with the aim of stimulating a new draining lymph node bed for each of the five administrations (Note: After the first 5 vaccinations, the vaccine may be administered in location of patient's preference). All nurses administering this vaccine will be trained to administer the doses intracutaneously prior to study implementation.

Intracutaneous injections are a combination of intradermal and subcutaneous injection. The maximum volume which can be administered intradermally is 0.1 ml and the maximum volume administered subcutaneously is considered to be 1-2 ml. Intracutaneous injections are a combination of the standard subcutaneous (many drugs) and intradermal (like a TB test) routes which are in routine use throughout the hospital. Drug will be administered using a 25G or smaller needle of ¼ to ⅝ inches in length.

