Treatment Plan: Vaccine Booster Cycles:

Cycles 8, 12, 16, 20, 24...														
Day	1	2	3	4	5	6	7	8	9	10	...	15	...	28
CDX-1410	X													
Poly ICLC	X													
Decitabine (DAC)	X	X	X	X	X									
Nivolumab (NIVO)	X													

Treatment is intended for an outpatient setting. However, at the investigator's/physician's discretion, the participant may receive treatment as an inpatient, if deemed necessary.

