11.5 Evaluations Performed on Day 15 of each Cycle

- Vital signs
- Hematology: CBC with manual differential (see Section 11.4)
- Chemistry: CMP, LDH, uric acid, amylase and, lipase (see Section 11.4)
- CDX-1401/poly-ICLC administration (Day 15 of every cycle for the *first 4 cycles*: thereafter, to be given on *Day 1 of every 4th cycle* as a booster (i.e. on Day 1 of cycles 8, 12, 16, 20, 24).
- Nivolumab administration (Day 15 for *first 4 cycles*: thereafter, to be given on *Day 1 of every 4th cycle*)
- Adverse events

11.6 Evaluations Performed Specifically at End of Cycle 1

- Endocrine Function Evaluation: TSH and blood glucose
- Bone Marrow Aspirate and Biopsy (**Note:** At the end of Cycle 1, if a bone marrow aspirate is not able to be done, a bone marrow biopsy may be performed instead). In Addition:
 - Study Bone marrow samples for T-cell and methylation and gene expression studies (Section 11.11.2)
- The following cardiac safety tests will be performed at the end of Cycle 1 and as clinically indicated:
 - Cardiac Safety Markers: Troponin-I, CK-MB, BNP
 - ECG
- Adverse events
- Urinalysis

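### The Appendix J grid marks the vaccine booster on Day 1 of cycles 5, 9, 13, but its own note 10, Sections 10.1.1 and 11.5 and the booster calendar name cycles 8, 12, 16: an 84-day difference in dosing date

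*Combined protocol and SAP*

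**What the plan says.** Appendix J is the schedule to which the opening of Section 11 and Section 11.10 send the reader. Its row "CDX-1401/ Poly-ICLC injection" has three marks: Day -14, Day 15 of each cycle, and the column "Day 1 of Cycle 5 and every 4 th cycle thereafter". Section 11.7 spells that last visit out as cycles 5, 9, 13, 17 and lists no vaccine among its procedures. The vaccine row is blank in the column for Day 1 of each cycle, so nothing in the grid stands for Day 1 of cycles 8, 12 or 16.

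Four other places give a different list:

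- Note 10 of Appendix J, attached to the mark in question: "day 1 of every 4th cycle as a booster (i.e. on day 1 of cycles 8, 12, 16, 20, 24".
- Section 10.1.1: the vaccine will "be administered on Day 1 of every 4th cycle as a booster (i.e. on day 1 of cycles 8, 12, 16, 20, 24".
- Section 11.5: "i.e. on Day 1 of cycles 8, 12, 16, 20, 24".
- The booster calendar in Section 10.1.3: "Cycles 8, 12, 16, 20, 24".

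The companion calendar in Section 10.1.3 groups cycles 5-7, 9-11, 13-15 and so on as cycles without vaccine. Sections 10.1 and 10.2 (the latter for the expansion cohort) put the booster in every fourth cycle without naming cycles. Section 10.1 also describes a 28-day cycle as including "and 1 vaccination (day 15"), although its first paragraph limits Day 15 dosing to the first four cycles, five vaccines in all.

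**The concern.** The protocol counts every fourth cycle in two ways: from cycle 5 for marrow and response (5, 9, 13), and in multiples of four for boosters (8, 12, 16). The grid puts a booster mark in the column for the first count, so a cell and its own footnote give different dates. The two lists share no cycle, and the column's cycles are ones that the calendars show without vaccine.

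Two things are at stake. One is the dosing date itself, in a document that sites use as their working schedule. The other is the secondary endpoint in Section 8.2, NY-ESO-1-specific T-cell and antibody response. Section 19.4 analyses change from baseline at designated time points that are not tied to days since vaccination. If patients were dosed under different readings, the same nominal visit would fall at very different distances from the last vaccine.

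**Working it through.** This is calendar arithmetic; no power or sample-size formula is involved.

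**Inputs.** Cycle length 28 days, primary series on Day -14 and Day 15 of cycles 1-4, and dosing window +/-7 days (Section 10.1). Booster cycles 5, 9, 13, 17 from the Appendix J column, or 8, 12, 16, 20 from note 10, Sections 10.1.1 and 11.5 and the calendar. Correlative blood on Day 1 and Day 15 from cycle 5 (Section 11.11.1). Study marrow on Day 1 of cycle 5 and of every fourth cycle after it (Section 11.11.2). Cycles are assumed to run without delay.

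**Formula.** Study day = (cycle - 1) x 28 + day.

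**The plan's own figure first.** The primary series falls on days -14, 15, 43, 71 and 99. That is five doses, which agrees with Section 10.1.

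**Booster dates.**

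| Booster | Column heading | Note 10 and calendar | Difference |
|---|---|---|---|
| 1st | C5D1 = 4 x 28 + 1 = 113 | C8D1 = 7 x 28 + 1 = 197 | 84 |
| 2nd | C9D1 = 225 | C12D1 = 309 | 84 |
| 3rd | C13D1 = 337 | C16D1 = 421 | 84 |

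The difference is 3 x 28 = 84 days each time. The nearest two dates from the different lists (cycle 8 and cycle 9) are 28 days apart, so the +/-7 day window cannot absorb the discrepancy.

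**Last primary dose (day 99) to first booster.** 113 - 99 = 14 days by the column; 197 - 99 = 98 days by note 10.

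**Days since last vaccine at pre-dose samples.**

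| Sample | Column heading | Note 10 and calendar |
|---|---|---|
| C5D1 | 113 - 99 = 14 | 113 - 99 = 14 |
| C5D15 | 127 - 113 = 14 | 127 - 99 = 28 |
| C8D1 | 197 - 113 = 84 | 197 - 99 = 98 |
| C9D1 | 225 - 113 = 112 | 225 - 197 = 28 |
| C13D1 | 337 - 225 = 112 | 337 - 309 = 28 |

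The sample days are the same in both columns of the table; only the interval from the last vaccine changes. The first post-series sample (C5D1) is unaffected. The difference is 14 days from C5D15 to C8D1, and 84 days at C9D1 and C13D1, which are marrow visits.

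**The case against.** The best counter-argument is that the cell corrects itself. The mark carries note 10, and note 10 names cycles 8, 12, 16. The grid relies on footnotes elsewhere too: the same note restricts the Day 15 mark to cycles 1-4, and note 10b does the same for nivolumab. Four places agree on one list, and no sentence anywhere names 5, 9, 13 as booster cycles. A site would have to overlook both the footnote and the calendars to dose at cycle 5. At most two sites take part, and Section 6 has every patient's records reviewed at least every two weeks. Much of this stands: it makes divergence unlikely and lowers the severity. It does not remove the fault, because the heading and the note on one cell still give different dates, and Sections 10.1 and 10.2 do not settle which applies.

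Some stronger readings are tempting, but the documents do not support them:

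- A reader might take the Day 15 clause in Section 10.1 as one vaccination in every cycle, hence 20 doses over cycles 5-24. The same section limits Day 15 dosing to the first four cycles, so this is loose wording in a summary sentence.
- A reader might see a further conflict in note 5 of Appendix J, "day 1 of each 4th cycle (cycles 5" and later. That is a label for the treatment phase, parallel to the cycles 1-4 label before it, and cycles 8, 12, 16 satisfy it.
- A reader might infer that the immune samples shift. They do not; blood and marrow dates are fixed to the cycle. Under either list each booster has a draw before dosing and another 14 days later, so recorded dose dates would allow the blood data to be interpreted.

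**Conclusion.** The contradiction is real and should be corrected before sites rely on the grid. Its size is 84 days per booster, and 112 against 28 days from last vaccine to the pre-dose samples at cycles 9 and 13. These figures assume 28-day cycles without delay.

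The harm is conditional: it arises only if a site follows the column heading rather than the note and calendars. Patients' immune data become hard to compare only if some are dosed under one reading and some under the other. The window for dose-limiting toxicity closes by Day 1 of cycle 2 (Section 8.1), well before any booster, so the primary analysis is untouched. Total vaccine exposure would differ little: both lists give five boosters over cycles 5-24, and a patient stopping during cycles 5-7 would differ by one dose. This is an inconsistency in the operative schedule, not a flaw in the design. Which booster list is right is for the sponsor to say.

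**What to change.** Reconcile the Appendix J vaccine row with note 10, Sections 10.1, 10.1.1, 10.2 and 11.5 and the Section 10.1.3 calendars, so that all show the one booster list the sponsor chooses. Give boosters their own column in Appendix J with the cycle numbers written out, and remove the vaccine mark from any column that does not match. Put the same explicit list in Sections 10.1 and 10.2. As a tidy-up, align the Day 15 vaccination clause in Section 10.1 with the cycles already stated there.

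The cost is one column and a few clauses. No sample-size, power or analysis text changes.

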2. INFORMED CONSENT

- Informed consent must be obtained by the **site Investigator/designee** from any participants wishing to participate, **prior to any procedures or treatment**.
- An informed consent template is provided by RPCI and can be amended to reflect institutional requirements.
- All consent changes **must** be reviewed by RPCI Network Office prior to submission to the site IRB.
- The informed consent must be IRB approved.
- Always check that the most up to date version of the IRB approved consent is being used.
- Within 5 business days, notify the RPCI Network Office of all participant withdrawals or consent to limited study participation and appropriately document the discontinuation and the reason(s) why.

3. PARTICIPANT REGISTRATION

The participant completes the Gender, Race, and Ethnicity Form and this is placed in the study binder.

RPCI does not grant exceptions to eligibility criteria.

Phase 1 Protocol Registration Instructions

Contact the RPCI Network Monitor to verify that a slot is available in the open cohort when a participant has been identified. **Do not have the participant sign consent prior to verifying an open slot.**

- After the participant signs consent, the Subject Screening and Enrollment Log must be faxed or emailed to the RPCI Network Monitor within 1 business day. The RPCI Network

PROTOCOL TITLE: I 49217 - Phase 1 CDX-1401/ Poly-ICLC +Decitabine +Nivolumab in
Patients with MDS or Low Blast Count AML

Monitor will confirm receipt of the Subject Screening and Enrollment Log and email the participant ID number.

- When the participant has met eligibility, a signed eligibility checklist and other requested documentation will be faxed or emailed to the RPCI Network Monitor.
- Within 1 business day of receipt of the eligibility check list, the RPCI Network Monitor will fax or email the cohort assignment and dose level.
- An email must be sent by the site to confirm receipt of the cohort assignment and to provide the planned treatment start date.

4. STUDY DEVIATIONS

- If a deviation has occurred to eliminate hazard, this must be reported to the RPCI Network, site IRB and any other regulatory authority involved in the study.
- ALL study deviations will be recorded on the **Study Deviation Log**.
- Participants inadvertently enrolled with significant deviation(s) from the study-specified criteria will be removed from the study, at the discretion of the Principle Investigator.

5. STUDY DOCUMENTATION

- Study documents must be filled out completely and correctly. Ditto marks are not allowed.
- If an entry has been documented in error put a single line through the entry and initial and date the change. The RPCI Network Monitor must be able to read what has been deleted.
- Do **NOT** use white-out, magic marker, scratch-outs.
- Do **NOT** erase entries.
- Use only black ink for documentation on the accountability form and any other study forms.
- It is the responsibility of RPCI to inform the Investigator/ institution as to when these documents no longer need to be retained. If, for any reason, the Investigator desires to no longer maintain the study records, they may be transferred to another institution, another investigator, or to RPCI upon written agreement between the Investigator and RPCI.

